10.3 Statistical Approaches to Outcome Analyses

This document contains information that is privileged or confidential and may not be disclosed unless such disclosure is required by applicable laws and regulations. The information in this document is the property of Apple Inc. and may not be reproduced, published, or disclosed to others without written authorization from Apple Inc.

There are no pre-specified statistical hypotheses in this clinical study. Descriptive statistics and 95% confidence intervals will be presented using available data as detailed below.

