10.3.3 Subgroup Analyses

The proportions and 95% confidence intervals for the primary outcomes (study objectives 1a and 1b) will be performed separately by age group (<55, 55-64, ≥ 65), sex, and race/ethnicity, cohort status determined at enrollment, and cohort status determined throughout the observations period (e.g., received an IRN during patch wear, received an ECG app-Inconclusive classification during patch wear). Chi-squared tests will be performed to determine if these proportions differ significantly by subgroup.

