This proportion will be estimated as the ratio of the number of participants in the EAS who have atrial fibrillation or atrial flutter of at least 30 seconds duration on patch wear and received an ECG app-Inconclusive status before enrollment, divided by the number of participants in the EAS who received an ECG app-Inconclusive status before enrollment. An exact 95% two-sided confidence interval will also be presented. We will also describe the

number of participants who received an ECG app-Inconclusive status before enrollment with arrhythmias other than atrial fibrillation.

Objective 2c Analysis

This proportion will be estimated as the ratio of the number of participants who have atrial fibrillation or atrial flutter of at least 30 seconds duration on patch wear who are greater than 65 years of age at enrollment divided by the number of participants enrolled who are greater than 65 years of age at enrollment using the EAS. An exact 95% two-sided confidence interval will also be presented. We will also describe the number of participants who are 65 years of age or older at enrollment with arrhythmias other than atrial fibrillation. A similar proportion will be presented for those less than 65 years of age at enrollment.

Sensitivity and Sub-analyses

The proportions and 95% confidence intervals for Objectives 1a and 1b will be performed separately by age group (<55, 55-64, ≥ 65), sex, race/ethnicity, cohort status determined at enrollment, cohort status determined during patch wear (e.g., received an IRN during patch wear, received an ECG app-Inconclusive classification during patch wear) and selected medical history conditions (e.g., ever diagnosed you with atrial fibrillation or atrial flutter, or ever had a stroke, Transient Ischemic Attack (TIA) or “Mini Stroke”). Chi-squared tests will be performed to determine if proportions differ significantly by subgroup.

Baseline demographics and medical history, survey results, and adverse events will be summarized using descriptive statistics for the FAS. Baseline demographics and medical history will also be summarized for participants in the FOG.

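### At least ten subgroup chi-squared tests on Objectives 1a and 1b are to be read for significance with no alpha, multiplicity control or exploratory label, in a study that states it has no hypotheses

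*Combined protocol and SAP*

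**What the plan says.** - **Protocol 10.3:** "There are no pre-specified statistical hypotheses in this clinical study". Results are to be descriptive, with 95% confidence intervals. Protocol 10.5 and SAP 1.3 repeat that the study is not designed to test hypotheses.
- **Protocol 10.3.3 (Subgroup Analyses):** the primary proportions are broken down by age group, sex, race/ethnicity, "cohort status determined at enrollment, and cohort status determined throughout the observations period". Then: "Chi-squared tests will be performed to determine if these proportions differ significantly by subgroup".
- **SAP 4.3 (Sensitivity and Sub-analyses):** "The proportions and 95% confidence intervals for Objectives 1a and 1b will be performed separately by age group", followed by "sex, race/ethnicity, cohort status determined at enrollment", "cohort status determined during patch wear (e.g., received an IRN during patch wear" and other in-wear examples, and "selected medical history conditions (e.g., ever diagnosed you with atrial fibrillation or atrial flutter, or ever had a stroke" or TIA). The paragraph ends: "Chi-squared tests will be performed to determine if proportions differ significantly by subgroup".
- **SAP Table 2:** seven medical-history conditions are available, so the examples in SAP 4.3 do not close the list. Race/ethnicity has nine response categories.
- **Not found in either document:** a significance level for these tests, an adjustment or testing order, or a statement that they are exploratory.

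**The concern.** The plan says that it tests nothing, then orders tests whose stated purpose is to decide whether AF proportions differ significantly. These are the only significance tests named in the plan. Elsewhere the SAP does limit inference: SAP 4.2 rules out statistical tests of baseline measurements by age group, and SAP 4.5 calls the longer AF-duration definitions tertiary. The subgroup tests carry no such limit. An analyst following the text would compare each p-value with a conventional cut-off and report whatever passes.

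Protocol 1.2 says that the findings should help to inform how the features may best be used and how future research is designed. A chance difference by sex, race/ethnicity or stroke history, reported as significant, could influence both.

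**Working it through.** **The plan's own figure.** The documents state no error rate for the subgroup tests, so there is none to reproduce. The design figure is a 95% interval no wider than 0.10 with 400 returned patches per group (SAP 1.3). The Gaussian width at a proportion of 0.5 is 2 × 1.96 × √(0.25/400) = 0.098, which agrees. That figure does not depend on the subgroup tests.

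**Number of tests** (one per factor and objective, two objectives):

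| Family | Factors | Tests |
|---|---|---|
| Protocol 10.3.3 list | 5 | 10 |
| SAP 4.3, medical history as one factor | 6 | 12 |
| SAP 4.3, AF history and stroke/TIA separate | 7 | 14 |
| SAP 4.3 without cohort status: age, sex, race/ethnicity, AF history, stroke/TIA | 5 | 10 |
| Sex and race/ethnicity only | 2 | 4 |

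Cohort status at enrollment partly defines Objectives 1a and 1b, so one might leave it out. With both cohort-status factors removed, the SAP list still gives 10.

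**Chance of at least one false positive.** Assumptions: each test is two-sided at 0.05 (the documents give no level), and all nulls in the family are true. For K independent tests the chance is 1 − 0.95^K:

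- K = 4: 1 − 0.95^4 = 18.5%
- K = 10: 1 − 0.95^10 = 40.1%
- K = 12: 1 − 0.95^12 = 46.0%
- K = 14: 1 − 0.95^14 = 51.2%

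**Effect of correlation.** Participants with both an IRN and an ECG app AFib result count in both objectives, and the sample size allows for 50% overlap. The 1a and 1b tests of one factor are therefore positively correlated, which lowers these figures. With correlated normal statistics:

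- K = 10, correlation 0.5 within each 1a/1b pair and independence between factors: about 38%.
- K = 10, correlation 0.5 among all tests: about 29%.
- K = 4, correlation 0.5 among all tests: about 16%.
- K = 14, correlation 0.5 among all tests: about 35%.

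**Direct simulation.** Five factors and two objectives were simulated under the global null, with 400 exclusive participants per group, AF at an assumed 40% and assumed subgroup shares. The rate was about 41% with no shared participants, 37% with 400 shared and 36% with 800 shared.

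**With adjustment.** Holm's strictest threshold for 10 tests is 0.05/10 = 0.005. Under independence the family-wise rate is then 1 − 0.995^10 = 4.9%.

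**The case against.** The best defence is that the study is already non-confirmatory. Three sections disclaim pre-specified hypotheses, the design target is interval width, and the tests appear only under subgroup or sensitivity headings. No decision, stopping rule or stated claim depends on a subgroup p-value. This stands, and it limits how serious the point is. It does not remove it, because the instruction to judge significance is explicit and the disclaimer does not say how to read the p-values.

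A second objection is that a global null is implausible. Patch-detected AF may well differ by prior AF diagnosis, age or stroke history. Protocol 1.1 itself links AF to stroke, and age has its own objective (2c). A positive test on those factors need not be false. This also stands. It is why the 4-test figure of 16% to 19% belongs beside the 10-test figure. That lower figure is still more than three times 0.05.

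A reader might infer that the plan carries a fixed false-claim risk of about 37%, or of more than a third. The documents do not support that. They state no level, and a figure near 37% needs 0.05 per test, an assumed overlap and every null true. With stronger correlation the 10-test value falls to 29%.

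**Conclusion.** The point holds as a matter of wording and interpretation. At least 10 tests (10 in the protocol, 12 to 14 in the SAP) are to be read for significance on the primary proportions, without a level, multiplicity control or exploratory label. This conflicts with the statement that there are no hypotheses.

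If each test is judged at 0.05, the chance of at least one false statement is about 29% to 40% for 10 tests with all nulls true, and about 16% to 19% if only sex and race/ethnicity are null. The ranges reflect the correlation between tests, which the documents do not fix.

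It would be wrong to infer that the primary results are compromised. The estimates and intervals for Objectives 1a and 1b do not use these tests. The change should be made before analysis, but it is not a design flaw.

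**What to change.** Replace the chi-squared sentence in protocol 10.3.3 and SAP 4.3 with:

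> Subgroup results for Objectives 1a and 1b are exploratory. Proportions with 95% confidence intervals will be reported for every listed subgroup, including cohort status, which is reported without a test. One overall chi-squared test per factor and objective will be done for age group, sex and race/ethnicity and, in the SAP, history of AF and history of stroke/TIA. All these p-values will be reported, Holm-adjusted across the full pre-specified family (two-sided 0.05), and no difference will be called significant on an unadjusted p-value.

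Close the SAP's tested medical-history list at the two conditions already named, and report any other condition without a test. The SAP family is then 5 × 2 = 10 tests. The protocol should refer to that family, so that only one adjustment exists.

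Three features of the wording matter:
- The family is fixed in advance and every p-value is reported, so it cannot shrink to the tests that someone chooses to show.
- One overall test per factor avoids up to 9 × 8 / 2 = 36 pairwise race/ethnicity comparisons per objective.
- The cohort-status estimates that both documents promise are kept.

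The cost is an edit to two documents, with no new data. The downside is lower power for each subgroup test (strictest threshold 0.005), for which the study makes no power claim.

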7.4.2 Procedures for ECG patch wear

The BioTelemetry ePatch Monitor will be used for ambulatory ECG monitoring. The battery life with a single channel recording is 7 days. The participant will be instructed to wear the ePatch for up to 7 days. However, the data collected from a participant will be considered adequate for a participant with a minimum analyzable time of 1 hour.

BioTelemetry will send participants, via courier, an ambulatory ECG monitoring kit containing one sensor and two adhesive patches. If the adhesive patch is no longer functional, the sensor

This document contains information that is privileged or confidential and may not be disclosed unless such disclosure is required by applicable laws and regulations. The information in this document is the property of Apple Inc. and may not be reproduced, published, or disclosed to others without written authorization from Apple Inc.

can be moved to the backup adhesive patch. At the end of the recording period, the participant will be required to mail the monitor back to BioTelemetry using the supplied prepaid mailer.

In the event it is discovered that the participant never received the ePatch due to a shipping error or became lost in transit, then BioTelemetry will issue a second ePatch to that participant. Any subsequent loss of ePatches will not be replaced.

Approximately 14-20 days after enrollment it is expected that most participants will have completed wearing the patch for up to 7 days and will have returned the patch to BioTelemetry via a provided tracked USPS mailer. The ambulatory ECG monitor should be received by BioTelemetry within 45 days from enrollment. Those who return patches beyond 45 days after enrollment or do not begin wearing their patch within 14 days of patch shipment will be included in the fall-out subgroup, however they will still be eligible for a follow-up visit with the Study Telehealth Provider. Those who never return the ambulatory ECG monitor will also be placed in the fall-out subgroup.

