8.2 Adverse Events (AEs)

This document contains information that is privileged or confidential and may not be disclosed unless such disclosure is required by applicable laws and regulations. The information in this document is the property of Apple Inc. and may not be reproduced, published, or disclosed to others without written authorization from Apple Inc.

The Study Safety Monitoring Desk is responsible for determining whether the adverse event occurred and is related to the IRN feature, ECG app on Apple Watch, ePatch, or associated with participation in the study.

Possible AEs include the following:

- Skin rash due to wearing the ambulatory ECG monitor (ePatch);
- Skin itchiness due to wearing the ambulatory ECG monitor (ePatch);
- Blister due to wearing the ambulatory ECG monitor (ePatch);
- Skin rash on wrist due to wearing the Apple Watch;
- Pressure artifacts on wrist due to wearing the Apple Watch;
- Signs or symptoms related to use of the IRN feature or ECG app on Apple Watch. The common signs and symptoms include stress and anxiety and associated symptoms that may include dizziness, depression, palpitations, tremors, sleep difficulty, and shortness of breath.

The following occurrences are not to be regarded as AEs:

- Underlying (pre-existing) symptoms or diseases, unless there is an increase in severity or frequency during the course of the investigation;
- Receipt of an IRN;
- Detection of atrial fibrillation or other irregular heartbeat through the IRN feature or ECG App;
- Detection of atrial fibrillation or other irregular heartbeat through ePatch;
- Pre-planned procedure(s);
- Complaint about iPhone or Apple Watch functionality;
- Failure of the participant to regularly wear the Apple Watch or to wear the ePatch
- Apple Heart Study 1.2 app, IRN feature, ECG app, and ePatch functionality issues that do not allege an adverse event

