3. ANALYSIS SETS

The Full Analysis Set (FAS) will consist of all enrolled participants who complete the informed consent process. This analysis set will be used to summarize subject demographics, medical history, adverse events, self-reported health status, diagnosis, and contact with the health care provider.

The ePatch Eligibility Analysis Set (EEAS) will consist of those in the FAS deemed eligible to receive an ePatch at Study Visit #1. This analysis set will be used to assess Objective 2a.

The ePatch Analysis Set (EAS) will consist of all those in the EEAS who receive and return an ePatch with at least 1 hour of usable data and who do not belong to the Fallout Subgroup. This analysis set will be used to assess Objectives 1a, 1b, and 2b and 2c. We will repeat these analyses in the EEAS as a sensitivity analysis using appropriate methods for handling missing data.

The Fallout Subgroup Analysis Set (FOG) will consist of participants who enroll and complete the informed consent process but otherwise do not complete the study. Reasons for study incompleteness include; failure to contact Study Telehealth Provider within 30 days of enrollment, being deemed ineligible at Study Visit #1 for ePatch wear due to emergent symptoms, ePatch not returned within 45 days of enrollment, failure to start wearing ePatch within 14 days of shipment, unable to verify at Study Visit #1 a study eligible IRN or ECG-app notification, study withdrawal (i.e., withdrawal of consent), or lost to follow-up (i.e., death). We will present demographic and medical history information for this analysis set.

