Additional analyses may be performed to gain further insight into the relationships between receiving notifications or app-based classifications and ePatch data. Importantly, we will additionally evaluate use of the IRN and ECG app features and behavioral response to notifications as captured in the 15 day PRO. Similarly, we will evaluate behavioral response to engaging a healthcare provider as captured in the 60 day PRO by relevant participant characteristics.

To understand the sensitivity of our findings for study objectives utilizing the EAS that requires at least 1 hour of useable data from participants in the EEAS, we will vary the requirement that participants with less than 1 hour of wear time be considered as missing their ECG data. We will also conduct additional sensitivity analyses considering the following alternative minimum wear times: 6 hours, 1 day, 2 days, and 5 days.

Adverse Events

A participant will be counted once for a reported AE even if the participant had multiple occurrences of that AE. We will summarize the proportion of participants reporting anxiety and rash in the EEAS and EAS. All AEs will be collected; however, these AEs are of most interest to the study device (anxiety) and are highest risk in the study (rash).

Adverse Events	N EEAS	% EEAS	N EAS	% EAS
Anxiety				
Rash				

The participant incidence of all serious adverse events will be presented for each analysis set by age group and overall.

Age group, yrs	N SAEs	N unique participants with SAEs	SAEs/participants with SAEs
< 55			
55-64			
65+			
Overall			

Analysis of Fall-Out Subgroup

The FOG (a subset of the FAS) will include participants who are enrolled but otherwise do not complete the study. Possible reasons are listed in Section 3. We will describe baseline characteristics for this group and for those in the FOG that have completed the PRO, we will report rates of contact with a non-study healthcare provider.

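### SAP 4.3 tabulates rash in the EEAS and EAS, neither of which is the set of ePatch wearers, and does not say which rash is counted

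*Combined protocol and SAP*

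**What the plan says.** The adverse event part of SAP 4.3 plans: "We will summarize the proportion of participants reporting anxiety and rash in the EEAS and EAS". The table shell has one row for anxiety and one for rash, with a number and a percentage for each set. Rash is chosen because the SAP regards it as the greatest risk of taking part; the term is not defined further.

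SAP 3 defines the sets:

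- EEAS: "The ePatch Eligibility Analysis Set (EEAS) will consist of those in the FAS deemed eligible to receive an ePatch at Study Visit #1". Receipt or wear is not required.
- EAS: members of the EEAS who "receive and return an ePatch with at least 1 hour of usable data and who do not belong to the Fallout Subgroup".
- Fallout Subgroup: the reasons include "ePatch not returned within 45 days of enrollment, failure to start wearing ePatch within 14 days of shipment", as well as Visit #1 contact later than 30 days, withdrawal and loss to follow-up.

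Protocol 7.4.2 provides for undelivered patches: "In the event it is discovered that the participant never received the ePatch due to a shipping error or became lost in transit", one replacement is sent and later losses are not made good. On non-returners it says: "Those who never return the ambulatory ECG monitor will also be placed in the fall-out subgroup". Protocol 7.4.1 lets participants with a late Visit #1 still receive a patch.

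Protocol 8.2 lists rash, itchiness and blister from the ePatch as three possible events, and a fourth separately: "Skin rash on wrist due to wearing the Apple Watch". Protocol 8.0 has the safety desk judge relatedness, with the ePatch as one of the named devices. SAP 3 and 4.3 also summarize adverse events for the FAS.

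**The concern.** A reader of the final table will want to know how often wearing the patch caused a skin reaction. That rate needs the people who put a patch on as its denominator, and no analysis set in the plan is defined that way. The EEAS is too wide for this purpose. The EAS was built for the rhythm outcome, so its entry rules concern usable data and timing, not exposure. The FAS summary is wider than the EEAS, because it includes people never cleared for a patch.

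The row label raises a second question. If Rash means any rash, patch and wrist reactions share one line and the figure cannot be assigned to either device. Itch and blister have no line in this table.

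What is at stake is the interpretation of one descriptive safety figure, for the event that the SAP itself singles out.

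**Working it through.** The plan states no rash rate, so there is no figure to reproduce. The check compares the sets with patch exposure and then shows the arithmetic under assumed inputs.

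**Sets against exposure**

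| Participant | Applied a patch? | EEAS | EAS |
|---|---|---|---|
| Eligible, patch never received or never applied | No | In | Out |
| Worn, under 1 hour of usable data | Yes | In | Out |
| Worn, returned after 45 days or never | Yes | In | Out |
| Worn, started more than 14 days after shipment | Yes | In | Out |
| Worn after a late Visit #1 | Yes | In | Out |
| Worn, then withdrew | Yes | In | Out |
| Worn and returned on time, at least 1 hour usable, no fallout reason | Yes | In | In |

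Subtracting the EAS count from the EEAS count gives the rash cases among eligible people outside the EAS, but not how many of those people wore a patch. A per-wearer rate therefore cannot be recovered from the two columns.

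**Inputs (all assumed)**

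- w, share of the EEAS who wore a patch: 65% to 95%. The plan allows about 35% attrition but does not say how much falls between eligibility and wear.
- d, share of wearers outside the EAS: 5% to 15%.
- r0, patch rash in retained wearers: 5%.
- r1, patch rash in dropped wearers: 5%, 20% or 40%.

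**Formulas**

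- Per-wearer rate = (1 − d) × r0 + d × r1
- EEAS rate = w × per-wearer rate
- EAS rate = r0

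**Results, patch rash only**

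1. EEAS: the rate is 0.65 to 0.95 times the per-wearer rate, whatever r1 is. A 5% per-wearer rate reads 0.65 × 5% = 3.25% to 0.95 × 5% = 4.75%.
2. EAS, exclusions unrelated to rash (r1 = 5%): per-wearer rate 5.0%, EAS 5.0%, ratio 1.00. There is no bias.
3. EAS, d = 5%, r1 = 20%: 0.95 × 5% + 0.05 × 20% = 5.75%; ratio 5/5.75 = 0.87.
4. EAS, d = 15%, r1 = 20%: 0.85 × 5% + 0.15 × 20% = 7.25%; ratio 5/7.25 = 0.69.
5. EAS, d = 15%, r1 = 40%: 4.25% + 6% = 10.25%; ratio 5/10.25 = 0.49.
6. If dropped wearers had less rash, the EAS would read high. With d = 15% and r1 = 0 the per-wearer rate is 4.25% and the ratio is 5/4.25 = 1.18.
7. Both columns together, w = 75% with item 4: per wearer 7.25%, EEAS 0.75 × 7.25% = 5.4%, EAS 5.0%. The columns need not bracket the per-wearer rate.

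**If wrist rash is counted in the same row**

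With 5% patch rash in wearers and an independent wrist rash v, any rash = 1 − 0.95 × (1 − v). For v = 1%, 2% and 3% this is 5.95%, 6.9% and 7.85%, or 1.19, 1.38 and 1.57 times the patch-only rate.

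Dilution and mixing pull in opposite directions. On the EEAS with w = 85% and v = 2%: 1 − (1 − 0.85 × 0.05) × 0.98 = 6.2%, above the 5% per-wearer risk. With w = 65% and v = 1%: 1 − (1 − 0.65 × 0.05) × 0.99 = 4.2%, below it.

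**The case against.** The strongest reply has four parts.

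- **The EEAS is a legitimate denominator.** It contains every eligible wearer, so its numerator can be complete, and it gives a valid rate per person cleared for a patch. This stands. A reader might infer that the plan has no valid denominator at all; the documents do not support that. What is missing is the per-wearer rate.
- **The EAS bar is low.** It asks for 1 hour of usable data out of up to 7 days. Someone who removes the patch because of a rash on day 2 and returns it on time remains in the EAS. The timing exclusions are logistical and nothing in the documents links them to rash. This stands too. A reader might infer that both columns understate the risk. For the EAS that needs an association the documents do not show, and wrist rash in the row could raise either column.
- **Mixing is not stated.** The SAP sentence can be read as meaning patch rash. Mixing is an inference from an undefined label beside two separate rash items in protocol 8.2. The definition is still absent.
- **Other safeguards exist.** The SAP says that all adverse events are collected, they are summarized for the FAS, and relatedness to the ePatch is judged. So the data for a split exist, but the table does not use them, and the FAS is no closer to exposure. The fall-out analysis describes baseline characteristics and provider contact, not adverse events.

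The study tests no pre-specified hypothesis and this table feeds no objective, which limits the weight of the point.

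**Conclusion.** The point holds in a limited form. Neither column of the rash table is a rate per ePatch wearer. The EEAS dilutes such a rate by exactly the share who wore a patch. The EAS departs from it only if being dropped is associated with rash. The undefined row may add wrist rash and raise the figure.

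The net direction is unknown and the size cannot be derived from the documents. The ratios above (0.65 to 0.95 for the EEAS; 0.49 to 1.00 for the EAS over the assumed range of r1, or above 1 if dropped wearers had less rash; 1.19 to 1.57 for mixing) rest wholly on assumed inputs and show scale only.

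This is a minor improvement to a descriptive safety table. It changes no endpoint, analysis set or primary result.

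**What to change.** In the SAP 4.3 adverse event table:

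1. Keep the EEAS column and add an 'ePatch wearers' column. Define a wearer as anyone with any recording on a returned patch, whatever its duration, start date or return date. Restrict the numerator to the same people.
2. Report ePatch skin reactions in participants with no returned recording separately, as a count or a sensitivity rate.
3. Replace the Rash row by 'ePatch skin reaction (rash, itch, blister)' and 'Apple Watch wrist rash (FAS)'. Assign events from the reported description and the relatedness determination already made. The devices named in protocol 8.0 do not include the watch hardware, so the wrist row will rest mainly on the description.

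The wearer definition must not depend on adverse event reports. Visit #2 follows return and reading of the patch, so a non-returner would normally be known as a wearer only by reporting an event, and would then always be a case. As an assumed illustration, take 900 returners with 4% rash (36 cases) and 100 non-returning wearers with 40% (40 cases). The true rate is 76/1000 = 7.6%. Admitting non-returners only through their reports gives 76/(900 + 40) = 8.1%. The proposed column gives 36/900 = 4.0% with the other 40 cases shown beside it, which is why item 2 is needed.

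Cost: one more row and one more column, from patch recordings and event records already collected. Wear remains unknown for non-returners, and wearers who report nothing are missed under any denominator; a footnote should say both.
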